11.0 Subject Disposition

The number and percentage of subjects who completed all screening assessments and enrolled in the study and who didn't complete all screening assessments and didn't enroll in the study and a breakdown of the corresponding reasons for not enrolling in the study, and members of each analysis set will be presented. The number and percentage of subjects who completed and who withdrew from the study prematurely and a breakdown of the corresponding reasons for withdrawal will also be presented. Analysis set, screening data, and study completion data will be listed by subject.

12.0 Protocol Deviations

Protocol deviations will be collected and reported per PRA's Protocol Deviation Management Standard Operating Procedure (SOP) and relevant Work Instruction (WI). Subject-level deviations will be extracted and pulled into the study tabulation model (SDTM) dataset from PRA's Clinical Trial Management. Deviations that have been reported and coded as "Important" will be listed by subject.

13.0 Demographic and Baseline Characteristics

13.1 Demographics

Subject demographics at screening will be summarized by renal function groups. The summary will include the subjects' age (years), sex, race, ethnicity, weight (kg), height (cm), body mass index (BMI) (kg/m^2) and baseline eGFR value. Demographics will be summarized for the Safety Set, PK Concentration Set and PK Parameter Set, if all sets are equivalent then only Safety Set will be presented.

All demographic data as collected during the screening visit will be listed by subject.

13.2 Medical History

Medical history, categorized by preferred term according to MedDRA, will be listed by subject.

13.3 Other Baseline Characteristics

Substance use (illegal drug, tobacco and alcohol) will be listed by subject.

Childbearing potential will be listed by subject.

Non-compliance to in- or exclusion criteria (if any) will be listed by subject.

14.0 Concomitant Medications

Concomitant medications collected on the eCRF as defined by the protocol will be categorized by medication group and subgroup according to WHO Drug Dictionary. All concomitant medications will be listed by subject. Medications with an end date prior to the first dose of study drug will be considered prior medications and will be noted in the listing. If the end date (e.g. partial or missing date) does not confirm that the medication was stopped prior to first dose the medication will not be flagged as prior.

15.0 Treatment Compliance and Exposure

The number and percentage of subjects receiving each dose of study drug will be summarized by renal function group.

Exposure data will be listed by subject.

16.0 Pharmacokinetic Analyses

16.1 Pharmacokinetic Variables

Concentrations of apraglutide will be collected in plasma.

PK parameters of apraglutide will be calculated for plasma.

16.2 Plasma Pharmacokinetic Summaries

16.2.1 Plasma Concentrations

Plasma concentrations of apraglutide below the quantifiable limit (BQL) will be set to 0 in the computation of mean concentration values. Descriptive statistics (number of subjects, mean, geometric mean, SD, coefficient of variation [%CV], median, min, and max) will be used to summarize the plasma concentrations by renal function group at each scheduled timepoint.

Linear (+/-SD) and semi-logarithmic (+SD) plots of the arithmetic mean plasma concentration by scheduled sampling time will be provided by renal function group. These plots will show time in hours. The plots will present all calculated means and will include a reference line for the lower limit of quantification (LLOQ).

Linear and semi-logarithmic plots of the individual plasma concentration by actual sampling time will be provided by subject (one subject per page). These plots will show time in hours. Individual plots will use the BQL handling procedure described below for "Plasma Pharmacokinetic Parameters".

All individual subject plasma concentration data will be listed by subject.

16.2.2 Plasma Pharmacokinetic Parameters

Plasma PK parameters for apraglutide will be estimated using non-compartmental methods with WinNonlin®. The PK parameters will be estimated from the concentration-time profiles, and AUCs will be calculated using linear up / log down method. The points to be included in the λ_z range will be determined by the pharmacokineticist after inspection of the semi-log concentration-time profiles. At least 3 points will be required to be used. The C_{max} data point will not be included.

In estimating the PK parameters, BQL values will be set to zero. Actual sampling times, rather than scheduled sampling times, will be used in all computations involving sampling times. If the actual time is missing, the scheduled time will be substituted and flagged.

The following flags will be used to include parameters that meet the predefined criteria for summary and analysis.

Criteria Name	Criteria
Extrapolation	AUC%Extrap <= 20%
Regression	Adj Rsq >= 0.8
Lz1	Lz_Start (parent only) >= 2*Tmax
Span	Span > 2

Note: Flags will be applied to parameters prior to derivation of additional parameters in SAS and will be used to include derived parameters as well.

Parameter	Description	SAS Programming Notes	Summary Statistic Reporting Precision*
Cmax	Maximum plasma concentration. Observed peak analyte concentration obtained directly from the experimental data without interpolation, expressed in concentration units	Cmax from WNL	3 significant digits
Tmax	Time to maximum plasma concentration. First observed time to reach peak analyte concentration obtained directly from the experimental data without interpolation, expressed in time units.	Tmax from WNL	2 decimal places
AUClast	Area under the concentration-time curve (time 0 to time of last quantifiable concentration).	AUClast from WNL	3 significant digits
AUCinf	Area under the concentration-time curve from time 0 extrapolated to infinity.	AUCINF_obs from WNL To be included in analysis/summaries if the following criteria are met: 
 • Extrapolation, • Regression 	3 significant digits
AUC0-7days	Area under the concentration-time curve from time 0 to Day 7 postdose inclusive. Equivalent to AUC0-168h	AUC0-168h from WNL From summary file To be included in analysis/summaries if the actual time for the Day 7 timepoint has a time deviation < 10%.	3 significant digits

T-HALF	Terminal elimination phase half-life expressed in time units. T- HALF, will be calculated as $\ln(2)/Lz$, where Lz is as defined below.	HL_Lambda_z from WNL To be included in analysis/summaries if the following criteria are met: 
 • Extrapolation • Regression • Lz1 • Span 	3 decimal places
CL/F	Apparent clearance after extra-vascular (EV) dose.	CL_F_obs from WNL To be included in analysis/summaries if the following criteria are met: 
 • Extrapolation, • Regression 	3 significant digits
Vz/F	Apparent volume of distribution after extra-vascular dose.	Vz_F_obs from WNL To be included in analysis/summaries if the following criteria are met: 
 • Extrapolation, • Regression 	3 significant digits

*Parameters with 'decimal place' precision will follow the General rule for summary statistics rounding with the number of decimal places noted as the starting point.

Descriptive statistics (number of subjects, mean, geometric mean, SD, %CV, median, min, and max) will be used to summarize the calculated PK parameters by renal function group. For Tmax, only median, min and max will be presented.

A scatter plot of individual (plus mean and median) PK parameters Cmax, AUClast and AUCinf by renal function group will be provided.

Box and whisker plots for individual subject parameters (AUCinf or AUClast and Cmax) will be constructed by renal function group and overlaid with geometric means.

All parameters will be listed by subject, parameters that meet the inclusion criteria will be accompanied by an indication that each is criteria met.

The following parameters are used for diagnostics and thus listed but not summarized.

Parameter	Description	SAS Programming Notes
AUC%Extrap	Percentage of AUCinf due to extrapolation from the last quantifiable concentration observed to infinity. $AUC\%Extrap = [AUCinf - AUClast]/AUCinf * 100$	AUC_%Extrap_obs from WNL
Adj Rsq	Goodness of fit statistic for the log-linear terminal elimination phase of the concentration-	Rsqr_adjusted from WNL

	time profile identified by least-squares linear regression and adjusted for the number of points (minimum of 3) used in the estimation of Lz.	
Lz	First-order rate constant associated with the terminal (log-linear) portion of the curve. Estimated by linear regression of time vs. log concentration	Lambda_z from WNL
Lz_Start	Lz_Start is the start time used in the regression for the determination of Lz.	Lambda_z_lower from WNL
Lz_End	Lz_End is the end time used in the regression for the determination of Lz.	Lambda_z_upper from WNL
Lz_N	Lz_N is the number of points used in the regression for the determination of Lz.	No_points_lambda_z from WNL
Span	The minimum number of half-lives needed for the Lz range to be acceptable.	Span from WNL

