 - k. Obtain blood pressure and heart rate measurements after at least 5 minutes of rest in a supine position (Section 7.2.3). One repeat measurement may be allowed at the discretion of the Investigator.
 - l. Injection site reaction assessments will be performed pre-dose and 4, 24, 48, 72, 96, 120, 144, and 168 hours post dose, as well as at Early Termination or Day 14.
 - m. Pharmacokinetic time points will be as follows: 0 (5 minutes pre-dose), 6, 12, 24, 28, 36, 40, 48, 60, 72, 96, 120, 144, 168, and 240 hours.
 - n. Subjects will be instructed to begin fasting 8 hours prior to Day 1 dose of apraglutide.
 - o. Changes since Screening.
 - p. Vitals signs on Day 1 at pre-dose, 1 hour and 4-hour time points. Vital Signs should be obtained within 45 minutes prior to dosing on Day 1.

1 Introduction

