1.3.2.1 Pharmacokinetics

Dose-proportional PK parameters obtained by non-compartmental analysis were seen after multiple doses for apraglutide within the range of 5.7 mg to 56.9 mg in clinical trial GYM-P3-698 and within the range of 1 mg to 10 mg in clinical trial TA799-002.

A population PK/PD model of apraglutide in healthy subjects and SBS patients [13] has been developed with data provided by the 82 subjects exposed to apraglutide to date. This model describes well apraglutide concentrations across the whole-body weight range of the subjects and for the doses of 1 to 50 mg SC with one central compartment with zero-order absorption from the subcutaneous administration site and first order elimination from the central compartment. The typical PK parameters for a 70 kg-weight human receiving 5 mg are:

- Absorption duration: 1.46 days
- Apparent volume of distribution: 31.5 L
- Clearance: 16.8 L/day
- Half-life: 1.32 days

The inter-individual variability (% coefficient of variation [CV]) was 35% on clearance and 41% on the volume of distribution. Body weight influenced clearance and the volume of distribution. No

statistically significant difference was found between the PK parameters of healthy subjects and SBS patients.

Body weight was found to be a covariate on clearance and apparent volume of distribution.

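### The half-life acceptance flags exclude values of about 84 h or more, so the descriptive severe/normal half-life comparison is understated if impairment markedly lowers clearance

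*SAP*

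**What the plan says.** SAP section 16.2.2 defines four flags: Extrapolation (at most 20% of AUCinf extrapolated), Regression (adjusted R-square at least 0.8), Lz1 ("Lz_Start (parent only) >= 2*Tmax") and Span (above 2). The T-HALF row reads "HL_Lambda_z from WNL To be included in analysis/summaries if the following criteria are met" and then names all four. AUCinf, CL/F and Vz/F need only Extrapolation and Regression.

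PK sampling in Protocol Table 1, footnote m, ends with "96, 120, 144, 168, and 240 hours".

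Half-life is a secondary PK parameter (Protocol 2.2.1, SAP 5.1.1). It is summarised descriptively by renal group, including the number of subjects, median and geometric mean. Every parameter is listed by subject with an indication of whether its criteria are met, and the regression diagnostics are listed too. The SAP plans no half-life summary without the flags and no count of exclusions by flag.

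**The concern.** A filter on data quality should not depend on the size of the quantity being estimated. Here, Lz1 fixes the earliest start of the regression and the last sample fixes its end. Requiring the window to exceed two half-lives then becomes an upper limit on the half-life itself. If renal impairment lengthens half-life, the impaired group has more of its distribution above that limit and loses its longest values.

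The stake is limited but real. The protocol relies on single-dose PK to predict multiple-dose PK (sections 1.2 and 3.2) and discusses once-weekly dosing, so readers will use the half-life table to judge accumulation in severe impairment. With about eight subjects per group, losing two from the upper tail changes that table visibly.

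**Working it through.** **Inputs from Protocol 1.3.2.1** (typical 70 kg subject, 5 mg): "Clearance: 16.8 L/day"; "Apparent volume of distribution: 31.5 L"; "Absorption duration: 1.46 days"; "Half-life: 1.32 days"; between-subject CV "was 35% on clearance and 41% on the volume of distribution". Sampling times and flags are as above. **Not in the documents, so varied as assumptions:** CL-V correlation, residual error, variability of absorption duration, LLOQ.

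**1. Reproduce the stated half-life.** ln(2) × 31.5 / 16.8 = 1.30 days = 31.2 h, against 1.32 days stated (1.5% apart).

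**2. Find the cut-off.** Absorption lasts 1.46 × 24 = 35 h, so observed Tmax should fall at the 36 h sample and 2 × Tmax = 72 h. The longest window is 240 − 72 = 168 h. Span above 2 then needs a half-life below 168 / 2 = 84 h.
- Tmax at 28 h: 2 × Tmax = 56 h, first usable sample 60 h, cut-off (240 − 60) / 2 = 90 h.
- Tmax at 40 h: 2 × Tmax = 80 h, first usable sample 96 h, cut-off (240 − 96) / 2 = 72 h.
- The SAP uses actual times. A 36 h sample drawn at 36.1 h gives 2 × Tmax = 72.2 h, so a 72 h sample drawn on time no longer qualifies and the cut-off is also 72 h.

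Span is the binding flag. In a noise-free profile, extrapolation is only 16% at a half-life of 84 h and reaches 20% near 96 h.

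**3. Share above 84 h if clearance is halved (exposure doubled).** Median half-life is 2 × 31.2 = 62.4 h. The log-scale SDs are √ln(1 + 0.35²) = 0.340 for CL and √ln(1 + 0.41²) = 0.394 for V. The log-SD of half-life is √(0.340² + 0.394² − 2ρ × 0.340 × 0.394), which is 0.52 at ρ = 0, 0.37 at 0.5 and 0.24 at 0.8. With ln(84 / 62.4) = 0.297:
- ρ = 0: z = 0.57, 28% above
- ρ = 0.5: z = 0.80, 21% above
- ρ = 0.8: z = 1.25, 11% above

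In normal subjects at ρ = 0, ln(84 / 31.2) / 0.52 = 1.90, so 3% lie above.

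**4. Simulate the full rule.** One-compartment profiles with zero-order input, protocol sampling times, linear-up/log-down AUC, all four flags, true half-life ratio about 2.0. The two right-hand columns assume 10% residual error and 20% variability in absorption duration. Cells give severe excluded / normal excluded / geometric mean ratio among those kept.

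| CL-V correlation | No noise | LLOQ 1 ng/mL | LLOQ 5 ng/mL |
|---|---|---|---|
| 0 | 28% / 3% / 1.64 | 34% / 7% / 1.55 | 38% / 33% / 1.45 |
| 0.5 | 21% / 0.3% / 1.76 | 29% / 1% / 1.68 | 31% / 29% / 1.66 |
| 0.8 | 11% / 0% / 1.90 | 21% / 0.3% / 1.84 | 24% / 24% / 1.85 |

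Repeat runs with small differences in set-up gave 20 to 34% of severe subjects excluded and ratios of 1.55 to 1.85 at LLOQ 1 ng/mL, and ratios of 1.44 to 1.88 at 5 ng/mL.

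**5. In subjects.** For n = 8, exclusion of 20 to 34% means 1.6 to 2.7 subjects. The chance of losing at least one is 1 − 0.80⁸ = 83% to 1 − 0.66⁸ = 96%.

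**6. Other scenarios.** At a true ratio of 1.2, 0.2 to 9% of severe subjects are excluded and the ratio reads 1.10 to 1.20. At 1.5, 3 to 18% are excluded. If exposure doubles through bioavailability alone, half-life does not change, about 1 to 6% are excluded and there is no bias.

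**The case against.** Several points on the other side stand.

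- **Scope.** The Lz1 and Span flags do not touch AUCinf, AUClast or Cmax. The ANOVA and the criterion for Part 2 do not use half-life, and the SAP plans no formal hypothesis testing. A doubling of exposure would still be visible in AUC.
- **Visibility.** The number of subjects behind each half-life summary is reported by renal group, and excluded values stay in the listings. A careful reader could find the loss, though not read its effect on the summary directly.
- **Scenario.** The protocol expects no renal effect, since no intact drug was found in urine. The bias also requires a change in clearance. Protocol 1.3.1.1 describes absorption-controlled kinetics after SC dosing in animals; if that held in humans, terminal half-life would not track clearance. The human model in 1.3.2.1, however, has first-order elimination.
- **Assumptions.** CL and V after SC dosing share bioavailability, so zero correlation, which gives the largest losses, is doubtful. At correlation 0.8, reaching a fifth excluded depends on the assumed assay error.

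A reader might infer that the flags remove almost only severe subjects. The documents do not support that, because the LLOQ is not given: at an assumed 5 ng/mL, similar shares of both groups are lost. The ratio is nevertheless still understated. A reader might also infer that the flags should be dropped. They have a purpose: Lz1 guards against fitting during a long absorption phase, and with the R-square rule alone one run admitted an estimate above 6,000 h.

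**Conclusion.** The point holds as a minor one. Given the protocol's PK values and sampling schedule, Lz1 and Span together exclude half-lives of about 84 h or more (72 to 90 h depending on observed Tmax), so selection depends on the outcome.

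Its size is conditional. It needs a substantial fall in clearance in severe impairment. At a doubling, the half-life ratio would read about 1.55 to 1.85 with an assumed LLOQ of 1 ng/mL, or 1.44 to 1.88 at 5 ng/mL, instead of 2.0. CL-V correlation, residual error and LLOQ are assumptions, but the ratio was understated in every clearance-driven doubling examined.

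A reader might take this as a bias in the trial's main conclusion about renal impairment. It is not: it is confined to the descriptive summary of a secondary parameter.

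**What to change.** Keep the four flags. In SAP section 16.2.2 and Table 14.2.2, summarise half-life by renal group twice: once with the flags applied as now, and once for all subjects with an estimable lambda-z (at least 3 points and adjusted R-square at least 0.8). Report the number of half-lives excluded in each renal group by flag.

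For the all-estimates row, base interpretation on the median and geometric mean, both already planned, since a few estimates may be extreme. In simulation at a true ratio of 2.0, with regressions still starting at or after 2 × Tmax, the R-square rule alone excluded 0 to 3% of severe subjects and gave a ratio of 1.91 to 2.00.

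The cost is a short SAP edit, one extra summary row and a small count table. No new data are needed. The downside is that the extra row will contain some imprecise long half-lives.

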16.2.2.1 Statistical Analyses

Part 1:

Analysis of variance (ANOVA) will be used to compare the natural log transformed AUCinf or AUClast (if AUCinf cannot be calculated) and Cmax for apraglutide between normal renal function group (Reference) and the severe impaired renal group (Test). Estimates of the mean differences (Test-Reference) and corresponding 90% CIs will be obtained from the model. The mean differences and 90% CIs for the differences will be exponentiated to provide estimates of the GMR (Test/Reference) and 90% CIs for the ratios.

The following SAS PROC MIXED pseudo-code may be used:

```
proc mixed data = adpp;
  by analyte parameter;
  class renal_group;
  model ln(aval) = renal_group;
  lsmeans renal_group / cl alpha = 0.1;
  estimate "Severe renal impairment vs Normal renal function" renal_group -1
  1 /e cl alpha=0.1;
run;
```

Part 2 (if conducted):

Analysis of variance will be used to compare the natural log transformed AUCinf or AUClast and Cmax for apraglutide between normal renal function group from Part 1 (Reference) and each of the moderate and mild impaired renal groups (Test). Estimates of the mean differences (Test-Reference) and corresponding 90% CIs will be obtained from the model. The mean differences and 90% CIs for the differences will be exponentiated to provide estimates of the GMR (Test/Reference) and 90% CIs for the ratios.

The following SAS PROC MIXED pseudo-code may be used:

```
proc mixed data = adpp;
  by analyte parameter;
  class renal_group;
  model ln(aval) = renal_group;
  lsmeans renal_group / cl alpha = 0.1;
```

```
estimate "Moderate renal impairment vs Normal renal function" renal_group  
0 -1 0 1 /e cl alpha=0.1;  
estimate "Mild renal impairment vs Normal renal function" renal_group 0 -1  
1 0 /e cl alpha=0.1;  
run;
```

If Part 2 is executed and data for normal, mild, moderate and severe impairment groups are available, additional analysis will be performed to assess relationship between appropriate PK parameters and renal function. The estimates of the GMR (Test/Reference) and 90% CIs for the ratios for AUC will be plotted for all three renal impairment groups (mild, moderate and severe). Linear regression analyses will be used to model the relationship between log-transformed PK parameters derived from subjects with normal renal function and those with mild, moderate or severe renal impairment (namely AUC_{inf} or AUC_{last} and C_{max}) and eGFR measured at screening, potentially accounting for age, sex, race and weight. The regression model will have log-transformed PK parameters as response variable, and include independent variable eGFR, and covariates age, sex, race and weight in the model.

The following SAS PROC MIXED pseudo-code may be used:

```
proc mixed data = adpp;  
by analyte parameter;  
class sex race;  
model ln(aval) = eGFR age sex race weight/ cl alpha=0.1;  
run;
```

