Part 1 of clinical trial: A total of approximately 16 subjects will be enrolled in Part 1: approximately eight subjects with severe renal impairment (Cohort 1) and approximately eight subjects with normal renal function (Cohort 2) to ensure at least six evaluable subjects in each group. Subjects from the severe renal impairment group will be recruited first. The demographics will be pooled across enrolled subjects to determine an average value for age and weight in the severe impairment group. Subsequently, the healthy subjects will be recruited later such that each subject's age is within ±10 years and weight is within ±15 kg of the mean of the severe renal impairment group. Attempts will be made to maintain a similar male/female ratio composition between groups. Care will be taken when recruiting the healthy subjects such that the entire group is not of substantially different age or of substantially different body weight than the severely renally impaired subjects.

Criteria to proceed to Part 2: After evaluation from Part 1, Part 2 will be conducted if the point estimate of apraglutide area under the concentration-time curve from time 0 to infinity (AUC_{inf}, or to the time of the last quantifiable concentration (AUC_{last}), if AUC_{inf} cannot be calculated) geometric mean ratio (GMR) for the severe renal impairment group compared to the control group (normal renal function group) is ≥2.

If criterion is not met, the trial will stop after Part 1. If there are subjects who withdraw or discontinue treatment from the normal or severe renal impairment groups and who are considered to be non-evaluable with respect to the primary PK objective, replacement subjects can be enrolled at the discretion of the sponsor.

Part 2 of clinical trial: If the decision criterion to proceed to Part 2 is met, approximately eight subjects each with moderate (Cohort 3) and mild (Cohort 4) renal impairment will be enrolled to ensure at least six

[figure not shown]
evaluable subjects in each group. As in Part 1, renal impairment classification will be based on eGFR. Healthy subjects will not be enrolled in Part 2. Healthy subjects from Part 1 will be used as the control group of the moderate and mild renal impairment subjects.

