9.2.2 Treatment/Subject Grouping

Subjects will be assigned to one of the 4 renal function groups based on eGFR values at screening.

Label	Grouping
IMP	Apraglutide (TA799): a single 5 mg dose of apraglutide administered by SC injection to the abdomen.
Renal Function Group	Cohort 1: Severe Renal Impairment Cohort 2: Normal Healthy Match Cohort 3: Moderate Renal Impairment Cohort 4: Mild Renal Impairment

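### The ESTIMATE coefficients in the SAP's pseudo-code for the primary comparison cannot all match their labels under any one ordering of the renal groups

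*SAP*

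**What the plan says.** SAP 16.2.2.1 names the normal group as Reference and the impaired group as Test. It then states: "Estimates of the mean differences (Test-Reference) and corresponding 90% CIs will be obtained from the model". The differences are exponentiated to Test/Reference ratios. Protocol 8.3 gives the same direction.

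Each part then has a code block introduced by "The following SAS PROC MIXED pseudo-code may be used". Both blocks read the dataset adpp and declare `renal_group` as a class variable with no ORDER= option. The three contrasts are:

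- Part 1, severe vs normal: "Severe renal impairment vs Normal renal function' renal_group -1", continued on the next line by 1, so the coefficients are `-1 1`.
- Part 2, moderate vs normal: "0 -1 0 1 /e cl alpha=0.1".
- Part 2, mild vs normal: "Mild renal impairment vs Normal renal function' renal_group 0 -1", continued by 1 0, so the coefficients are `0 -1 1 0`.

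The SAP text does not give the values or sort order of `renal_group`. The nearest thing to an order is the grouping table in SAP 9.2.2: "Cohort 1: Severe Renal Impairment Cohort 2: Normal Healthy Match Cohort 3: Moderate Renal Impairment Cohort 4: Mild Renal Impairment". It is not described as the class-level order.

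The Part 1 ratio also carries a decision. Under SAP 6.0, Part 2 is conducted if the AUC geometric mean ratio (GMR) point estimate "for the severe renal impairment group compared to the control group (normal renal function group) is ≥2".

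**The concern.** PROC MIXED assigns ESTIMATE coefficients to class levels by position. The label is free text and does not affect the result. A line whose coefficients do not fit the level order therefore runs without error and prints a different comparison under the intended label.

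This is the only code the SAP offers for its primary comparison. If it is adapted with the coefficients left as printed, two kinds of error can follow. The severe-to-normal ratio and its interval can be reported as reciprocals, and that ratio is tested against the threshold of 2. In Part 2, the moderate and mild ratios can be exchanged, or a line can return a contrast that is not the labelled comparison with normal. An exchange is the harder error to see, because both figures are ratios to normal and may be of similar size.

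**Working it through.** **What each line requires**

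- Part 1, `-1 1`: the first level gets -1 and the second +1. To be severe minus normal, normal must come before severe.
- Moderate line, `0 -1 0 1`: normal must be second and moderate fourth.
- Mild line, `0 -1 1 0`: normal must be second and mild third.

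Together the Part 2 lines fix normal second, mild third and moderate fourth. That leaves severe first, ahead of normal, and contradicts Part 1.

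**Enumeration**

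Four groups can be ordered in 4! = 24 ways. Part 1 was treated as the two-level restriction of each order.

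| Line(s) matching the label | Orders out of 24 |
|---|---|
| Part 1 | 12 |
| Moderate | 2 |
| Mild | 2 |
| Both Part 2 lines | 1 (severe, normal, mild, moderate) |
| All three | 0 |

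If all four levels are present when the Part 1 line runs, it is right in 2 orders instead of 12, and all three lines still match in none. These counts show that the lines are inconsistent. They are not probabilities, because the orders are not equally likely.

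**What the natural codings return**

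| Level order | Part 1 line | Line labelled moderate | Line labelled mild |
|---|---|---|---|
| Cohort number (severe, normal, moderate, mild) | normal - severe | mild - normal | moderate - normal |
| Alphabetical (mild, moderate, normal, severe) | severe - normal (right) | severe - moderate | normal - moderate |
| eGFR descending (normal, mild, moderate, severe) | severe - normal (right) | severe - mild | moderate - mild |
| eGFR ascending (severe, moderate, mild, normal) | normal - severe | normal - moderate | mild - moderate |

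Both Part 2 lines are wrong in all four. Part 1 is right in two.

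**Illustration.** Assume true ratios to normal of 2.2 (severe), 1.6 (moderate) and 1.2 (mild). Cohort order prints 1/2.2 = 0.455, then 1.2 under the moderate label and 1.6 under the mild label. Alphabetical order prints 2.2, then 2.2/1.6 = 1.375 and 1/1.6 = 0.625.

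**Size of an uncaught Part 1 inversion**

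Inputs: 8 per group (SAP 6.0). The documents give no CV for AUC, so 35% is assumed, the inter-individual value for clearance in protocol 1.3.2.1.

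- Log-scale SD = sqrt(ln(1 + 0.35²)) = 0.340.
- SE of the log ratio = 0.340 × sqrt(2/8) = 0.170.
- 90% CI factor on 14 df = exp(1.761 × 0.170) = 1.349.
- An estimate of 1.50 has interval 1.50/1.349 = 1.11 to 1.50 × 1.349 = 2.02. Inverted, it prints as 0.67 (0.49 to 0.90).

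Inversion changes the Part 2 decision when the true-direction estimate is at least 2 (prints as at most 0.5, so the trial stops) or at most 0.5 (prints as at least 2, so Part 2 runs). On the normal log scale, P(change) = P(estimate ≥ 2) + P(estimate ≤ 0.5):

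| True GMR | 8 per group (SE 0.170) | 6 per group (SE 0.196) |
|---|---|---|
| 1.0 | <0.01% | 0.04% |
| 1.5 | 4.5% | 7% |
| 2.0 | 50% | 50% |
| 2.5 | 91% | 87% |

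At a true GMR of 2.5 with 8 per group, a CV of 25% gives 97% and a CV of 45% gives 85%. Every figure in this table is conditional on the inversion occurring and going unnoticed.

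**The case against.** The strongest defence is that the prose governs and is right, while the code is optional pseudo-code. It cannot be run verbatim, since a MODEL response cannot be written as ln(aval), so a programmer must rewrite it anyway. That stands: the defect is in the coding specification, and the estimand is unaffected. It does not make the printed lines correct, and they contradict both their labels and the prose beside them.

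Second, each block could be right alone if the two runs were coded differently: normal before severe in Part 1; severe, normal, mild, moderate in Part 2. This is possible, but nothing in the SAP specifies it. Both blocks share a dataset and a class variable, and the SAP says that the AUC ratios "will be plotted for all three renal impairment groups (mild, moderate and severe". One shared coding is the natural reading, though the joint plot does not strictly require it. The separate table shells or the dataset metadata might state an order. That would not help, because no single order rescues all three lines.

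Third, detection is likely. The same step prints group LSMEANS, and the /e option prints the coefficients. SAP 16.2.2 adds geometric means by group and box plots, and SAP 9.2.4.1 classes the PK parameter dataset as critical for QC. A clear inversion should be seen. An exchange of two similar ratios is less obvious.

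Finally, protocol 1.2 expects no renal effect on PK. If that is so, a changed decision is very unlikely (<0.01% with 8 per group) and the Part 2 lines may never be used. This limits the probable harm, but the reported ratio and interval would still be reciprocals at any estimate other than 1.

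**Conclusion.** The concern holds. The three printed contrasts are mutually inconsistent under any level order shared by the two parts, and under the SAP's own cohort numbering none returns its labelled comparison. This follows from the coefficients alone and needs no assumption beyond a shared order.

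The practical consequence is conditional. It requires that the coefficients be kept as printed and that the checks miss the error. The changed-decision figures also rest on the assumed 35% CV for AUC and matter only for true ratios near or above 2. The analysis model, the direction of comparison in the prose and the Part 2 rule are all correct. The code should be corrected before it is used, because it concerns the primary analysis and the correction costs almost nothing.

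**What to change.** Preferred: in both blocks, replace the ESTIMATE statements with differences against a named reference, `lsmeans renal_group / diff=control('<Normal level>') cl alpha=0.1`, filling in the actual value of the normal level. The result then does not depend on sort order.

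Alternative: state the level order in the SAP and align the coefficients with it.

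| Order | Severe vs normal (Part 1) | Moderate vs normal | Mild vs normal |
|---|---|---|---|
| Cohort 1 to 4 | `1 -1` | `0 -1 1 0` | `0 -1 0 1` |
| Alphabetical | `-1 1` (as printed) | `0 1 -1 0` | `1 0 -1 0` |

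The cost is three lines of SAP pseudo-code. The prose and the estimand stay as they are, and no protocol amendment is needed.
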